9.2.3.1.1 Time Period and Frequency for Collecting and Reporting Safety Event Information

9.2.3.1.1.1 Disease-related Events

Disease-related events are defined in [Appendix 4](#).

The investigator is responsible for ensuring that all disease-related events observed by the investigator or reported by the subject that occur after the first dose of investigational product through the safety follow-up visit/end of study are recorded using the Event CRF.

All serious disease-related events will be recorded and reported to the sponsor or designee within 24 hours. The investigator will submit any updated serious disease-related event data to the sponsor within 24 hours of it being available.

Disease-related events assessed by the investigator to be more severe than expected and/or related to the investigational product(s)/study treatment/protocol-required therapies, and determined to be serious, must be reported on the Event CRF as serious adverse events and recorded and reported per Section [9.2.3.1.1.3](#) and [Appendix 4](#).

Disease-related events pre-defined for this study are listed in [Appendix 11](#).

9.2.3.1.1.2 Adverse Events

The adverse event grading scale to be used for this study will be the CTCAE version 4.03 and is described in [Appendix 4](#).

The investigator is responsible for ensuring that all adverse events observed by the investigator or reported by the subject that occur from first dose of investigational product through the safety follow-up visit/EOS are reported using the Event CRF.

9.2.3.1.1.3 Serious Adverse Events

The investigator is responsible for ensuring that all serious adverse events observed by the investigator or reported by the subject that occur after signing of the informed consent through safety follow-up visit/EOS are reported using the Event CRF.

All serious adverse events will be collected, recorded and reported to the sponsor or designee within 24 hours, as indicated in [Appendix 4](#). The investigator will submit any updated serious adverse event data to the sponsor within 24 hours of it being available.

The criteria for grade 4 in the CTCAE grading scale differs from the regulatory criteria for serious adverse events. It is left to the investigator's judgment to report these grade 4 abnormalities as serious adverse events.

9.2.3.1.1.4 Serious Adverse Events After the Protocol-required Reporting Period

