
• Disease-related events are events (serious or non-serious) anticipated to occur in the study population due to the underlying disease. See Appendix 11 for a list of disease-related events. All serious disease-related events will be recorded and reported to the sponsor or designee within 24 hours.• Disease-related events that would qualify as an adverse event or serious adverse event:
○ An event based on the underlying disease that is worse than expected as assessed by the investigator for the subject's condition or if the investigator believes there is a causal relationship between the investigational product(s)/study treatment/protocol-required therapies and disease worsening, this must be reported as an adverse event or serious adverse event.• Disease-related events that do not qualify as adverse events or serious adverse events:
○ An event which is part of the normal course of disease under study (eg, disease progression in oncology or hospitalization due to disease progression) is to be reported as a disease-related event.

Definition of Adverse Event

Adverse Event Definition

• An adverse event is any untoward medical occurrence in a clinical study subject irrespective of a causal relationship with the study treatment.• Note: An adverse event can therefore be any unfavorable and unintended sign (including an abnormal laboratory finding), symptom, or disease (new or exacerbated) temporally associated with the use of a treatment, combination product, medical device or procedure.• Note: Treatment-emergent adverse events will be defined in the statistical analysis plan (SAP).

Events Meeting the Adverse Event Definition

- Any abnormal laboratory test results (hematology, clinical chemistry, or urinalysis) or other safety assessments (eg, electrocardiogram [ECG], radiological scans, vital signs measurements), including those that worsen from baseline, that are considered clinically significant in the medical and scientific judgment of the investigator (ie, not related to progression of underlying disease).
- Exacerbation of a chronic or intermittent pre-existing condition including either an increase in frequency and/or intensity of the condition.
- New conditions detected or diagnosed after study treatment administration even though it may have been present before the start of the study.

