- Signs, symptoms, or the clinical sequelae of a suspected drug-drug interaction.
- Signs, symptoms, or the clinical sequelae of a suspected overdose of either study treatment or a concomitant medication. Overdose per se will not be reported as an adverse event/serious adverse event unless it is an intentional overdose taken with possible suicidal/self-harming intent. Such overdoses are to be reported regardless of sequelae.
- The signs, symptoms, and/or clinical sequelae resulting from lack of efficacy will be reported as adverse event or serious adverse event if they fulfill the definition of an adverse event or serious adverse event. Also, “lack of efficacy” or “failure of expected pharmacological action” also constitutes an adverse event or serious adverse event.

Events NOT Meeting the Adverse Event Definition

- Medical or surgical procedure (eg, endoscopy, appendectomy): the condition that leads to the procedure is the adverse event.
- Situations in which an untoward medical occurrence did not occur (social and/or convenience admission to a hospital).
- Anticipated day-to-day fluctuations of pre-existing disease(s) or condition(s) present or detected at the start of the study that do not worsen.

Definition of Serious Adverse Event

A Serious Adverse Event is defined as any untoward medical occurrence that, meets at least 1 of the following serious criteria:	

• Results in death (fatal)	

• Immediately life-threatening The term "life-threatening" in the definition of "serious" refers to an event in which the subject was at risk of death at the time of the event. It does not refer to an event, which hypothetically might have caused death, if it were more severe.	

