Appendix 11. Disease Related Events Table

Below is a list of common Disease-Related Events. This list is not meant to be comprehensive. All serious disease-related events will be recorded and reported to the sponsor or designee within 24 hours.

Organ System	Disease Related Event
Skin	Scleroderma (superficial or fasciitis), lichen planus, vitiligo, scarring alopecia, hyperkeratosis pilaris, contractures from skin immobility, nail bed dysplasia
Mucous membranes	Lichen planus, non-infectious ulcers, corneal erosions/non-infectious conjunctivitis, xerostomia, keratoconjunctivitis sicca
GI tract	Esophageal strictures, steatorrhea, anorexia, malabsorption, weight loss, abdominal pain
Liver	None
GU tract	Vaginal stricture, lichen planus
Musculoskeletal /Serosa	Non-septic arthritis, myositis, myasthenia, polyserositis, contractures from joint immobilization
Hematologic	None
Lung	Bronchiolitis obliterans

Amendment 5

Protocol Title: A Phase 1b/2 Open-label Study Evaluating the Safety, Tolerability, Pharmacokinetics, Pharmacodynamics, and Efficacy of Efavaleukin Alfa in Adult Subjects With Steroid Refractory Chronic Graft Versus Host Disease

Amgen Protocol Number efavaleukin alfa 20160283

Amendment Date: 22 June 2021

Rationale:

The rationale for this protocol amendment is:

- To update the phase 1b part of the study to allow for continued access to efavaleukin alfa for up to an additional 156 weeks following week 102 (Q2W dose) or week 103 (QW dose) at the discretion of the Sponsor, following discussion and agreement between the principal investigator and medical monitor, for subjects who are responding to efavaleukin alfa (as assessed by week 104) and who wish to continue on treatment.
- Administrative and editorial updates.

Amendment 4

Protocol Title: A Phase 1b/2 Open-label Study Evaluating the Safety, Tolerability, Pharmacokinetics, Pharmacodynamics, and Efficacy of Efavaleukin Alfa in Adult Subjects With Steroid Refractory Chronic Graft versus Host Disease

Amgen Protocol Number efavaleukin alfa 20160283

Amendment Date: 08 December 2020

Summary of Changes:

- Remove the following assessments from the schedule of activities:
[REDACTED]

- Update and consolidate clinical experience information
- Updates to maintain consistency regarding criteria for the progressive disease visit
- Add permission for recreational drug use as per country regulations to exclusion criterion 214

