### **Overall summary of subject incidence of treatment-emergent adverse events and**

by preferred term and worst severity grade will be provided by anti-AMG592 and [REDACTED] status. Subject incidence of events of interest (standardized MedDRA queries and/or Amgen Medical Queries) will also be summarized according to their categories, preferred term, and worst severity grade. Events of interest could include but are not limited to Hypersensitivity, Tachyarrhythmias, Tachypnea, Hematopoietic Cytopenia, **Eosinophilic Disorder**, Leucocyte Changes, Infection and Infestation, Cytokine Release Syndrome, **Drug Related Hepatic Disorder**, and Injection Site Reaction. Number of episodes and duration of treatment-emergent injection site reactions will be further summarized.

Subject incidence of treatment-emergent adverse events identified by COVID-19 standardized MedDRA queries and serious adverse events occurring on or after the COVID-19 infection will also be summarized.

Subject incidence of disease related events and fatal disease-related events will be tabulated by system organ class and preferred term. They are defined for this study in [Appendix D](#).

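### Protocol Appendix 4 lets the same unrelated cGVHD worsening count as a disease-related event or as an AE/SAE, and no planned SAP table is insensitive to that choice

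*Protocol*

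**What the plan says.** **Primary endpoint.** Besides DLTs, the phase 1b primary endpoint is the incidence of treatment-related AEs, TEAEs and SAEs (Protocol 4.1, SAP 2.1).

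**Out of the AE category.** In Protocol Appendix 4, under "Disease-related events that do not qualify as adverse events or serious adverse events", an event in the normal course of the disease goes to the disease-related stream. The example extends to hospital admission: "hospitalization due to disease progression) is to be reported as a disease-related event".

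**The exception.** The bullet just before it sends worsening back to AE/SAE if it is "worse than expected as assessed by the investigator for the subject's condition", or if the investigator believes the study drug caused it.

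**Into the AE category.** The list of events that meet the AE definition, also in Appendix 4, includes "Exacerbation of a chronic or intermittent pre-existing condition including either an increase in frequency and/or intensity of the condition", with no carve-out for cGVHD. It then says that the clinical consequences of lack of efficacy are AEs if they meet the AE definition. A second sentence, without that condition, says that lack of efficacy itself "also constitutes an adverse event or serious adverse event".

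**The list of disease-related events.** Protocol 9.2.3.1.1.1 introduces it with "Disease-related events pre-defined for this study are listed in" Appendix 11. Appendix 11 says "This list is not meant to be comprehensive".

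**Analysis.** The TEAE definition in SAP 5.5 starts from events already classed as adverse events. SAP 9.6.2 gives serious, fatal and worst-grade tables for AEs. For the other stream it says: "Subject incidence of disease related events and fatal disease-related events will be tabulated by system organ class and preferred term".

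**The concern.** A subject whose cGVHD worsens on treatment, without the investigator finding the worsening unexpected or drug-related, fits more than one rule. Protocol 7.4.2.1.1 classes worsening that needs new immunosuppression as a treatment failure. That reads naturally as lack of efficacy and as exacerbation of a pre-existing condition, and also as the normal course of steroid-refractory disease. Appendix 4 gives no order of precedence, and no adjudication of the choice is described. The study is open-label, so the investigator files the event knowing the dose.

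The choice decides which table the event enters. Filed as an AE, it counts in TEAE incidence and, if the subject was hospitalised, in SAE incidence. Filed as disease-related, it appears only in a table that does not separate serious from non-serious events. With 3 to 6 DLT-evaluable subjects per cohort, a few filing decisions could create or hide a pattern of SAEs across doses.

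**Working it through.** **1. The plan's own figure.** The only stated number that rests on counting AEs is the chance of seeing at least one AE with a true incidence of 5% (Protocol 10.1.1, SAP 3.2): 87% with 40 subjects and 79% with 30. The formula is 1 − (1 − p)^n.
- n = 40: 1 − 0.95^40 = 87.1%.
- n = 30: 1 − 0.95^30 = 78.5%.

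Both reproduce. They presuppose that every occurrence is filed as an AE.

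**2. If a share f of such events is filed as disease-related.** The rate visible in the AE table becomes 0.05 × (1 − f). The documents give no value for f, so this range is an assumption. It applies only to event types that could plausibly be disease manifestations and are judged unrelated.

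| f | n = 40 | n = 30 |
|---|---|---|
| 0 | 87.1% | 78.5% |
| 10% | 84.1% | 74.9% |
| 20% | 80.5% | 70.6% |
| 30% | 76.0% | 65.7% |
| 50% | 63.7% | 53.2% |

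**3. Effect on incidence within a cohort.** One subject filed the other way moves subject incidence by 1/n:
- cohort of 6: 1/6 = 16.7 points;
- cohort of 3: 1/3 = 33.3 points;
- 30 subjects pooled: 1/30 = 3.3 points.

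For SAE incidence this requires that the event is serious and that the subject has no other SAE.

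**4. Which parts of the primary endpoint are exposed.**
- *DLTs:* every criterion in Protocol 7.4.1.2 requires relatedness to efavaleukin alfa, and related worsening must be an AE/SAE. Largely protected.
- *Treatment-related AEs:* protected for the same reason.
- *All-cause TEAEs and SAEs judged unrelated:* exposed. The worse-than-expected exception narrows the gap, but it is itself the investigator's judgement and does not settle the overlap with lack of efficacy.

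**5. Which tables would show the event either way.** SAP 9.6.2 provides AE tables (any, serious, related, leading to withdrawal, fatal, worst grade) and disease-related tables (all, fatal). All serious disease-related events must be reported to the sponsor within 24 hours (Protocol 9.2.3.1.1.1), so they are identifiable, yet none of these tables shows them. No table adds the two streams, so no incidence figure in this section stays the same whichever way an event was filed.

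**The case against.** The strongest reply is that the plan limits the problem in several places.

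- **Worsening is not excluded outright.** A reader might infer that Appendix 4 bars all disease worsening from the AE category. It does not: unexpected or drug-related worsening must be an AE/SAE, and the normal-course example is taken from oncology and does not name cGVHD. This stands and confines the issue to unrelated events.
- **Events are moved, not lost.** Both streams are recorded on the Event CRF, and SAP 9.6.1 includes disease-related events in the analysis of the primary safety endpoint. This stands.
- **Progression and death show elsewhere.** SAP 9.2 summarises reasons for stopping drug and leaving the study by treatment group. Protocol 8.1 and 8.2.2 list cGVHD progression, need for alternative therapy and death among those reasons. A reader might infer that deaths split over two tables cannot be reassembled; disposition gives at least a partial count. It does not show serious events that did not end treatment or participation.
- **The list is open on purpose.** A reader might call Appendix 11 a contradiction and want it closed. Appendix 4 defines the concept and the appendix gives common examples; the Amendment 4 summary records the non-inclusive wording as a deliberate clarification. At most, describing the events as pre-defined in Protocol 9.2.3.1.1.1 is loose. Closing the list would be a preference, not a correction.
- **No decision turns on these tables.** Phase 1b has no statistical hypothesis (SAP 2.2), and dose-level review uses all available safety data (Protocol Appendix 3). This limits the consequence to how safety is reported.

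What remains is the missing precedence rule and the lack of any summary unaffected by it.

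**Conclusion.** The point holds in a limited form. Appendix 4 has overlapping rules for unrelated, normal-course cGVHD worsening and no order of precedence. All-cause TEAE and SAE incidence by dose therefore depends partly on how each investigator files the event. DLT and treatment-related incidence are largely unaffected, so it would be wrong to conclude that the whole primary endpoint is at the mercy of filing.

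The size is 16.7 points of SAE incidence per refiled subject in a cohort of 6, provided that the event is serious and the subject has no other SAE. Overall TEAE incidence moves less readily, because a subject with any other TEAE is already counted. A reader might want to turn this into a number of subjects affected, but the documents give neither a rate of worsening nor a rate of discordant filing, so no such estimate is supported. The detection probabilities under f above 0 are illustrative for the same reason.

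**What to change.** 1. **SAP 9.6.2, by dose group.** Add the subject incidence of (a) serious disease-related events, and (b) AEs and disease-related events combined: any, serious and fatal. Count each subject once and apply the same treatment-emergent window to both streams. The combined rows do not depend on how a site filed the event, so they still help at the final analysis although the study is ending early.
2. **Grade 3 or higher, combined.** Add this where the Event CRF recorded a grade for disease-related events. Appendix 4 explicitly requires severity grading only for AEs and SAEs, so check the data first and state in a footnote how many disease-related events have no grade.
3. **Protocol Appendix 4.** Reconcile the normal-course rule with the exacerbation and lack-of-efficacy rules so that one takes precedence. Align Protocol 9.2.3.1.1.1, which covers upgrading only for serious events, whereas Appendix 4 covers AEs and SAEs. This will not refile past events, which is why the tables matter more.

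**Cost.** A few extra tables, mostly from data already recorded, and a short wording change. The combined figures will look less favourable because they include disease worsening; showing them beside the AE tables, with a label saying so, deals with that.

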1. SITE INFORMATION								
Site Number	Investigator				Country			
Reporter			Phone Number	()		Fax Number		
2. SUBJECT INFORMATION								
Subject ID Number	Age at event onset			Sex	Race	If applicable, provide End of Study date		
				□ F □ M				
If this is a follow-up to an event reported in the EDC system (eg, Rave), provide the adverse event term: _____ and start date: Day ____ Month ____ Year ____								
3. SERIOUS ADVERSE EVENT								
Provide the date the Investigator became aware of this information: Day ____ Month ____ Year ____								
Serious Adverse Event diagnosis or syndrome If diagnosis is unknown, enter signs / symptoms and provide diagnosis, when known, in a follow-up report List one event per line. If event is fatal, enter the cause of death. Entry of "death" is not acceptable, as this is an outcome.			Date Started	Date Ended	Check only if event occurred before first dose of IP Is event serious? Serious enter Serious Criteria code (see codes below)	Relationship Is there a reasonable possibility that the event may have been caused by IP or an Amgen device used to administer the IP?	Outcome of Event -Resolved -Not resolved -Fatal -Unknown	Check on if event is related to study procedure eg, biop
Day	Month	Year	Day	Month				
Serious Criteria: 01 Fatal 02 Immediately life-threatening			03 Required/prolonged hospitalization 04 Persistent or significant disability/incapacity			05 Congenital anomaly / birth defect 06 Other medically important serious event		
4. Was subject hospitalized or was a hospitalization prolonged due to this event?  No  Yes If yes, please complete all of Section 4								
Date Admitted Day Month Year				Date Discharged Day Month Year				
5. Was IP/drug under study administered/taken prior to this event?  No  Yes If yes, please complete all of Section 5								
IP/Amgen Device: <<IP/Device>>		Date of Initial Dose	Date of Dose	Dose	Route	Frequency	Action Taken with Product	Lot # and Serial # Lot # _____  Unknown Serial # _____  Unavailable / Unknown
<<IP/Device>> <<IP/Device>>		Day Month Year	Day Month Year				01 Still being Administered 02 Permanently discontinued 03 Withheld	
<<IP/Device>> <<IP/Device>>								Lot # _____  Unknown Serial # _____  Unavailable / Unknown
FORM-056006 Page 1 of 3 Version 7.0 Effective Date: 1 February 2016								

AMGEN Study # 20160283 AMG 592	Electronic Serious Adverse Event Contingency Report Form For Restricted Use											
			Site Number		Subject ID Number							
6. CONCOMITANT MEDICATIONS (eg, chemotherapy) Any Medications?  No  Yes If yes, please complete:												
Medication Name(s)		Start Date Day Month Year	Stop Date Day Month Year	Co-suspect  No  Yes	Continuing  No  Yes	Dose	Route	Freq.	Treatment Med  No  Yes			
7. RELEVANT MEDICAL HISTORY (include dates, allergies and any relevant prior therapy)												
8. RELEVANT LABORATORY VALUES (include baseline values) Any Relevant Laboratory values?  No  Yes If yes, please complete:												
Date Day Month Year	Test											
	Unit											
9. OTHER RELEVANT TESTS (diagnostics and procedures) Any Other Relevant tests?  No  Yes If yes, please complete:												
Date Day Month Year	Additional Tests				Results				Units			

Appendix 5. Contraceptive Guidance and Collection of Pregnancy and Lactation Information

Study-specific contraception requirements for females of childbearing potential are outlined in Section 6.2.

Female subjects of childbearing potential must receive pregnancy prevention counseling and be advised of the risk to the fetus if they become pregnant during treatment and after the last dose of protocol-required therapies.

Definition of Females of Childbearing Potential

A female is considered fertile following menarche and until becoming postmenopausal unless permanently sterile. Permanent sterilization methods include hysterectomy, bilateral salpingectomy, and bilateral oophorectomy.

Females in the following categories are not considered female of childbearing potential:

- Premenopausal female with 1 of the following:
 - Documented hysterectomy;
 - Documented bilateral salpingectomy; or
 - Documented bilateral oophorectomy.

Note: Site personnel documentation from the following sources is acceptable:

- 1) review of subject's medical records; 2) subject's medical examination; or
- 3) subject's medical history interview.

- Premenarchal female
- Postmenopausal female
 - A postmenopausal state is defined as no menses for 12 months without an alternative medical cause. A high follicle stimulating hormone (FSH) level in the postmenopausal range may be used to confirm a postmenopausal state in women not using hormonal contraception or hormonal replacement therapy (HRT). However, in the absence of 12 months of amenorrhea, a single FSH measurement is insufficient.
 - Females on HRT and whose menopausal status is in doubt will be required to use 1 of the non-hormonal highly effective contraception methods if they wish to continue their HRT during the study. Otherwise, they must discontinue HRT to allow confirmation of postmenopausal status before study enrollment

Contraception Methods for Female Subjects

Highly Effective Contraceptive Methods

Note: Failure rate of < 1% per year when used consistently and correctly.

- Combined (estrogen and progestogen containing) hormonal contraception associated with inhibition of ovulation (oral, intravaginal, or transdermal)
- Progestogen-only hormonal contraception associated with inhibition of ovulation (oral, injectable, implantable)
- Intrauterine device (IUD)
- Intrauterine hormonal-releasing system (IUS)
- Bilateral tubal ligation/occlusion
- Vasectomized partner (provided that partner is the sole sexual partner of the female subject of childbearing potential and that the vasectomized partner has received medical assessment of the surgical success)
- Sexual abstinence (defined as refraining from heterosexual intercourse during the entire period of risk associated with the study treatments; the reliability of sexual abstinence must be evaluated in relation to the duration of the trial and the preferred and usual lifestyle of the subject)

Unacceptable Methods of Birth Control for Female Subjects

Birth control methods that are considered unacceptable in clinical trials include:

- Periodic abstinence (calendar, symptothermal, post-ovulation methods)
- Withdrawal (coitus interruptus)
- Spermicides only
- Lactational amenorrhoea method

Collection of Pregnancy Information

Female Subjects Who Become Pregnant

- Investigator will collect pregnancy information on any female subject who becomes pregnant while taking protocol-required therapies through 6 weeks.
- Information will be recorded on the Pregnancy Notification Worksheet (see [Figure 12-2](#)). The worksheet must be submitted to Amgen Global Patient Safety within 24 hours of learning of a subject's pregnancy. (Note: Sites are not required to provide any information on the Pregnancy Notification Worksheet that violates the country or regions local privacy laws.)
- After obtaining the female subject's signed authorization for release of pregnancy and infant health information, the investigator will collect pregnancy and infant health information and complete the pregnancy questionnaire for any female subject who becomes pregnant while taking protocol-required therapies through 6 weeks of the study drug. This information will be forwarded to Amgen Global Patient Safety. Generally, infant follow-up will be conducted up to 12 months after the birth of the child (if applicable).

- Any termination of pregnancy will be reported to Amgen Global Patient Safety, regardless of fetal status (presence or absence of anomalies) or indication for procedure.
- While pregnancy itself is not considered to be an adverse event or serious adverse event, any pregnancy complication or report of a congenital anomaly or developmental delay, fetal death, or suspected adverse reactions in the neonate will be reported as an adverse event or serious adverse event. Note that an elective termination with no information on a fetal congenital malformation or maternal complication is generally not considered an adverse event, but still must be reported to Amgen as a pregnancy exposure case.
- If the outcome of the pregnancy meets a criterion for immediate classification as a serious adverse event (eg, female subject experiences a spontaneous abortion, stillbirth, or neonatal death or there is a fetal or neonatal congenital anomaly) the investigator will report the event as a serious adverse event.
- Any serious adverse event occurring as a result of a post-study pregnancy which is considered reasonably related to the study treatment by the investigator, will be reported to Amgen Global Patient Safety as described in [Appendix 4](#). While the investigator is not obligated to actively seek this information in former study subjects, he or she may learn of a serious adverse event through spontaneous reporting.
- Any female subject who becomes pregnant while participating will discontinue study treatment (see Section [8.1](#) for details).

Collection of Lactation Information

- Investigator will collect lactation information on any female subject who breastfeeds while taking protocol-required therapies through 6 weeks.
- Information will be recorded on the Lactation Notification Worksheet (see below) and submitted to Amgen Global Patient Safety within 24 hours of the investigator's knowledge of event.
- Study treatment will be discontinued if female subject breastfeeds during the study as described in exclusion criterion [220](#).
- With the female subjects signed authorization for release of mother and infant health information, the investigator will collect mother and infant health information and complete the lactation questionnaire on any female subject who breastfeeds while taking protocol-required therapies through 6 weeks after discontinuing protocol-required therapies.

Figure 12-2. Pregnancy and Lactation Notification Worksheet

AMGEN® Pregnancy Notification Worksheet

Fax Completed Form to the Country-respective Safety Fax Line

SELECT OR TYPE IN A FAX#

1. Case Administrative Information

Protocol/Study Number:

Study Design: Interventional Observational (If Observational: Prospective Retrospective)

2. Contact Information

Investigator Name
Phone Fax Site #
Institution
Address

3. Subject Information

Subject ID # Subject Gender: Female Male Subject DOB: mm / dd / yyyy

4. Amgen Product Exposure

Amgen Product	Dose at time of conception	Frequency	Route	Start Date
				mm  / dd  / yyyy 

Was the Amgen product (or study drug) discontinued? Yes No
If yes, provide product (or study drug) stop date: mm / dd / yyyy
Did the subject withdraw from the study? Yes No

5. Pregnancy Information

Pregnant female's LMP mm / dd / yyyy Unknown
Estimated date of delivery mm / dd / yyyy Unknown N/A
If N/A, date of termination (actual or planned) mm / dd / yyyy
Has the pregnant female already delivered? Yes No Unknown N/A
If yes, provide date of delivery: mm / dd / yyyy
Was the infant healthy? Yes No Unknown N/A
If any Adverse Event was experienced by the infant, provide brief details:

Form Completed by:
Print Name: Title:
Signature:  Date:

AMGEN® Lactation Notification Worksheet

Fax Completed Form to the **Country**-respective Safety Fax Line

SELECT OR TYPE IN A FAX#

1. Case Administrative Information

Protocol/Study Number: 20160283

Study Design: Interventional Observational (If Observational: Prospective Retrospective)

2. Contact Information

Investigator Name _____ Site # _____

Phone (____) _____ Fax (____) _____ Email _____

Institution _____

Address _____

3. Subject Information

Subject ID # _____ Subject Date of Birth: mm_____/dd_____/yyyy____/

4. Amgen Product Exposure

Amgen Product	Dose at time of breast feeding	Frequency	Route	Start Date
				mm_____/dd_____/yyyy____/

Was the Amgen product (or study drug) discontinued? Yes No

If yes, provide product (or study drug) stop date: mm_____/dd_____/yyyy____/

Did the subject withdraw from the study? Yes No

5. Breast Feeding Information

Did the mother breastfeed or provide the infant with pumped breast milk while actively taking an Amgen product? Yes No

If No, provide stop date: mm_____/dd_____/yyyy____/

Infant date of birth: mm_____/dd_____/yyyy____/

Infant gender: Female Male

Is the infant healthy? Yes No Unknown N/A

If any Adverse Event was experienced by the mother or the infant, provide brief details: _____

Form Completed by:

Print Name: _____

Title: _____

